7.3.2 Blood and Serology Specimens

For measurement of antibodies in serum, 6ml peripheral venous blood will be collected into an appropriate blood collection tube, and then processed to obtain serum.

For assessment of T-cell responses, 40-50ml ml of peripheral venous blood will be collected into tubes containing sodium heparin as an anti-coagulant, mixed by inverting gently several times and then processed to obtain PBMC which will be frozen and stored for future batch immunogenicity analysis.

7.4 Procedures for Assessing Safety and Tolerability

7.4.1 Adverse Event Assessment

Information on adverse events will be collected through a structured interview at scheduled visits as indicated in **Table 5**.

The investigator will record the diagnosis or the symptoms if a diagnosis is not apparent, the date of onset and the date of resolution if appropriate. For events not specified in the tables in study specific toxicity grading table (**Appendix 2**) the severity will be determined according to the FDA guidance (2007)

<http://www.fda.gov/downloads/BiologicsBloodVaccines/GuidanceComplianceRegulatoryInformation/Guidances/Vaccines/ucm091977.pdf>

The seriousness of the event and its relationship to vaccine will be determined by the investigator according to the definitions provided in **section 8**. All of this information will be recorded in the adverse event CRF.

7.4.2

General Examination and Vital Signs

General examinations will be done at screening and on dosing days, as per **section 7.2.1** (height and weight at screening only). General examinations at other visits per **Table 5** will be done only if clinically indicated. Assessment of vital signs (blood pressure, pulse, respiratory rate and oral temperature) will be performed at all visits up to Week 22.

7.4.3

Routine Laboratory Parameters and Urinalysis

A pregnancy test will be performed by analysis of a urine sample for Human Chorionic Gonadotrophin (HCG) collected from women of child-bearing potential at screening, the day of each immunisation and at the final safety visit (Week 22). The analysis will be conducted by a member of the study team.

Peripheral blood and urine will be collected and analysed, as described in **section 7.2.3**, for the following parameters at the time points specified in **Table 5**, and at additional time points if indicated to further evaluate or follow up adverse events:

7.4.3.1 Blood

- Creatinine, AST, ALT, alkaline phosphatase, total bilirubin, glucose
- Hb, total WCC, neutrophils, lymphocytes, platelets

7.4.3.2 Urine

- protein, ketones, blood, leukocyte esterase, and nitrites – by dipstick

A urine specimen will be sent to the laboratory if the level of protein, blood, leukocyte esterase or nitrites is considered clinically relevant.

Various local and systemic adverse events are known to be associated with licensed vaccines, and are referred to as '**solicited adverse events**'. These include disturbances in routine laboratory parameters, and are described in **table 2** below.

Information on solicited adverse events will be collected on the day of each immunisation (pre-immunisation, and at 10 and 60 minutes post-immunisation), at a safety call the day after each immunisation and for the following 7 days through a structured interview and examination according to the schedule.

In addition systemic laboratory adverse events will be collected through routine laboratory testing according to the schedule. These will be recorded on the appropriate CRF page.

Participants will also be asked to complete a diary card recording solicited adverse events that start within 7 days of each immunisation.

Table 2: Solicited Adverse Events

Type	Event
Local AEs (immunisation site)	Discomfort Redness Swelling (soft) Induration (hard) Blisters
Systemic Clinical AEs	Abnormally raised temperature Chills Myalgia/flu-like general muscle aches Malaise (excess fatigue) Headache Nausea Vomiting
Systemic Laboratory AEs	Abnormalities in: Creatinine, AST, ALT, alkaline phosphatase, total bilirubin, glucose Hb, total WCC, neutrophils, lymphocytes, platelets

The events will be **graded** according to the study specific toxicity table (see **Appendix 2**).

Relationship to study product, which is defined in **section 8**, will be recorded in the immunisation CRF but not on the diary card, on the assumption that any of these events starting within 7 days of an immunisation are at least possibly related. If the onset is beyond 7 days, the event will be recorded on the adverse event CRF and a relationship determined by the investigator reviewing the event.

7.4.5 Non-solicited Adverse Events

Non-solicited AEs starting from the first vaccination until the final safety visit (Week 22) will be captured and reported on the adverse event CRF. When making a non-solicited AE enquiry, staff should ask a non-leading question such as 'how have you been feeling?'

7.4.6 Follow-up of Adverse Events and Pregnancy

The Investigator will make every effort to monitor all adverse events, regardless of severity, until resolution or stabilisation, and to obtain documentary evidence of the outcome of pregnancy, in order to report this on the CRF during the trial.

7.4.7 Serious adverse events

A serious adverse event is defined in **section 8**.

All serious adverse events should be reviewed by the Principal Investigator for the clinical centre, and discussed at the next Trial Management Group call (**section 16.1**).

The assessment should include consideration of whether or not to discontinue dosing or to withdraw a participant from the trial.

7.4.8 Tolerability of vaccination using the electroporation devices

A tolerability questionnaire will be given to subjects to complete after each vaccination with EP. They will score pain at the time of vaccine injection, the time of electrical stimulation, and 10 and 30 min afterwards, using a 10-point scale. They will also be asked general questions about acceptability, and asked for their comments.

7.5 Criteria for Stopping Treatment Groups or Whole Trial

In the event of a SUSAR, the Chief Investigator should notify the sponsor within 24 hours of the event taking place, and the Chief Investigator will arrange for any necessary expert reviews to take place within 3 working days.

Further immunisations will be put on hold until the review is completed.

A component of any expert review will be to consider whether or not further immunisations should be discontinued in the individual, and/or the trial.

If 3 or more participants experience a grade 3 or 4 clinical or laboratory event (confirmed on attendance or repeat testing) not resolved within 72 hours and considered possibly, probably or definitely related to vaccine product, further immunisations will be put on hold and the Chief Investigator will call a meeting with the Trial Management Group (TMG) to review the safety data. If upon review of the safety data it is deemed appropriate to restart dosing, a substantial amendment with relevant data has to be submitted to the MHRA for approval. If an unscheduled TMG meeting is warranted, the Sponsor will be informed and the TMG asked to make a recommendation to the Chief Investigator and the Sponsor about continuing further immunisations.

At any time if the study is put on hold (for example following the occurrence of a SUSAR) the Regulatory authority has to be informed of the temporary halt and a substantial amendment with relevant data has to be submitted to the MHRA for approval in case a

decision to resume dosing is taken. The Sponsor reserves the right to stop the whole trial at any time.

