1.1.5 Objectives

Primary

- To evaluate the safety and immunogenicity of an HIV-1 DNA vaccine delivered via combined intramuscular and intradermal methods with and without electroporation, and boosted with CN54gp140 administered by intradermal injection with the aim of identifying optimal conditions capable of promoting enhanced antibody responses to HIV.

Secondary

- To compare the safety of the electroporation devices to standard intramuscular or intradermal injections

Exploratory:

- To describe qualitative differences between the different methods of delivery in terms of changes from baseline in overall magnitude and functionality of antibody

responses to the vaccines, and quantitative differences in cellular responses (CD4+ and CD8+ T cells)

- To evaluate the tolerability of vaccination using the electroporation devices

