2.2.5 Risks and Benefits

This is a Phase I exploratory study in healthy male and female volunteers.

HIV DNA plasmid-based vaccines are widely used alone and in combination regimens, including the multicentre EuroVacc trials EV01-3 in which we have been involved and which volunteers were given up to 12mg DNA over 12 weeks with no safety concerns. There is currently limited data available on the systemic use of CN54ENV DNA but our group is directly involved in the only trial using CN54ENV and CN54gp140 delivered IM in DNA-MVA-protein strategy (UKHVC SPOKE 003; EUDRACT: 2012-003277-26) initiated in July 2013 and now completed, for which our group have direct access to safety data as it becomes available.

While electroporation has been used in multiple studies, it has not been used to deliver this particular vaccine in humans before, but the supporting preclinical study (CR 525569), was shown to be well tolerated in rabbits. Furthermore, a previous Phase I trial to use electroporation (EP) for the delivery of a DNA vaccine for HIV demonstrated increased immunogenicity in the absence of associated safety concerns [44] [62]. A more recent study (HVTN 080) assessed a mixture of 3 expression plasmids encoding HIV-1 Clade B Env, Gag, and Pol delivered together with a DNA expressing IL-12 followed by EP with no associated safety concerns [63]). The vaccination schedules in this study are complex and on each visit volunteers will receive at least one vaccination with EP. There is an increased risk that retention to the trial will suffer as a result. The first Phase I trial to use EP for the delivery of a DNA vaccine for HIV has recently reported and observed an increase in immunogenicity. All the volunteers completed their immunisations, and adverse reactions were in line with licensed vaccines. In the ongoing healthy volunteer study (CUTHIVAC 001, EUDRACT 2011-003171-11), one participant elected to discontinue further immunisations due to pain and eight participants were subsequently randomised to EP and preceded without a problem.

There is no direct benefit to the volunteers. They will be reimbursed for their time and travel. Volunteers also derive the benefits of clinical screening and any follow up care for the time that they are enrolled in the study and afterwards where appropriate. As there is no placebo group, there is a risk that adverse events will be over-reported, but this should not influence grade and is not a concern at this stage of evaluation.

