6.1.5 Dose Modifications and Discontinuation

There are no planned modifications to dose, other than discontinuation.

The schedule may be modified if a participant has symptoms or signs on the day of scheduled immunisation, and the investigator considers it best to defer the immunisation. The participant will be asked to return for review within the window period of the scheduled immunisations (-3/+7 days from week 4, 8 and 20 for the second, third and fourth immunisations respectively).

A clinical investigator may decide to permanently discontinue dosing in a participant who has received one or more immunisations, if the investigator deems that continuing might compromise participant wellbeing or interfere with the achievement of the trial's objectives. Such a decision should only be taken in consultation with the Chief Investigator. Participants will be encouraged to continue to attend trial visits for sampling and safety monitoring.

Discontinuation of dosing is essential following a grade 3 or 4 clinical or laboratory event (confirmed on examination or repeat testing respectively) which is considered possibly, probably or definitely related to the vaccine and which did not resolve within 72 hours.

Provided the participant agrees they will continue to be followed up for the duration of the study and samples will be collected at the allotted times.

Dosing must be discontinued in participants who become pregnant or HIV infected.

Participants may decide to discontinue dosing. They will be encouraged to provide a reason, and to remain in follow-up. The appropriate CRF should be completed as soon as possible if a patient chooses to stop receiving vaccines or to withdraw from the trial, and within 24 hours of a decision being taken to discontinue a participant when that decision is informed by an adverse event (**section 8.1**).

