8.1 Definitions

The definitions of the EU Directive 2001/20/EC Article 2 based on the principles of ICH GCP apply to this protocol. These definitions are given below:

Adverse event

Any untoward medical occurrence in a subject to whom a medicinal product has been administered, including occurrences which are not necessarily caused by or related to that product.

The investigator will use the following criteria when deciding whether to report a laboratory parameter that falls outside the normal range according to the local laboratory guidelines as an adverse event:

- The test result is associated with relevant accompanying symptoms
- Additional diagnostic tests or medication are indicated
- As a consequence of the test result, an immunisation is delayed or further immunisations are discontinued
- The investigator considers the result to constitute an adverse event for any other reason

Adverse reaction

Any untoward and unintended response in a subject to an investigational medicinal product which is related to any dose administered to that subject.

'Related' means possibly, probably or definitely as defined below.

All solicited adverse events which start within 7 days of a vaccination will be automatically classified as an adverse reaction.

Unexpected adverse reaction

An adverse reaction, the nature or severity of which is not consistent with the information about the medicinal product in question set out in the Investigator's Brochure.

Serious Adverse Events (SAEs), Serious Adverse Reaction (SARs), Suspected Unexpected Serious Adverse Reactions (SUSARs)

Any adverse event, adverse reaction, or unexpected adverse reaction is considered to be a "serious" if it:

- Results in death
- Is life-threatening
- Requires hospitalisation or prolongation of existing hospitalisation
- Results in persistent or significant disability or incapacity
- Consists of a congenital anomaly or birth defect
- Any other medically important event

Notes:

- **'A threat to life'** refers to an event or reaction in which the patient was at risk of death at the time of the event; it does not refer to an event or reaction which hypothetically might have caused death had it been more severe.

If an AE is serious and unexpected and considered possibly, probably or definitely related to study product according to the classification below then it meets the criteria for a SUSAR and should be reported accordingly.

Relationship to study product

This can be classified as:

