Unrelated	adverse events that can be clearly explained by extraneous causes and for which there is no plausible association with study product, or adverse events for which there is no temporal relationship
Unlikely	adverse events that may be temporally linked, but which are much more likely to be due to other causes than study product and which do not get worse with continuing use of product
Possibly	adverse events that could equally well be explained by study product or other causes, which are usually temporally linked and may improve when not using study product but do not reappear when using study product
Probably	adverse events that are temporally linked and for which the study product is more likely to be the explanation than other causes, which may improve when not using study product
Definitely	adverse events that are temporally linked and for which the study product is the most likely explanation, which disappear or decrease when not using study product and reappear when using study product

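### Mandatory discontinuation (Protocol 6.1.5) and the three-participant hold (7.5) test relation to the vaccine and do not name electroporation, which leaves a narrow gap for severe events attributed to the device or procedure

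*Protocol*

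**What the plan says.** Two rules in the Protocol force action after a grade 3 or 4 clinical or laboratory event that is confirmed and has not resolved within 72 hours.

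- Section 6.1.5 stops dosing in the individual after an event "which is considered possibly, probably or definitely related to the vaccine".
- Section 7.5 acts once three or more participants have had such an event, if it is "considered possibly, probably or definitely related to vaccine product, further immunisations will be put on hold".

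Relatedness is graded in Section 8.1 against study product, and an adverse reaction is defined there as a response to an investigational medicinal product. An event is 'Unlikely' to be related if it belongs among those "which are much more likely to be due to other causes than study product". The lowest grade that counts as related, 'Possibly', covers "adverse events that could equally well be explained by study product or other causes". One class needs no judgement: "All solicited adverse events which start within 7 days of a vaccination will be automatically classified as an adverse reaction".

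On exposure, Section 2.2.5 says that "on each visit volunteers will receive at least one vaccination with EP"; Table 1 shows that this means the three DNA visits, since the week-20 protein dose has no EP. The secondary objective in Section 1.1.5 is "To compare the safety of the electroporation devices to standard intramuscular or intradermal injections".

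**The concern.** What differs between the three groups is where EP is applied; the DNA doses and routes are the same. The two mandatory rules nevertheless test relation to the vaccine, and neither they nor the causality scale mentions the device or the procedure. Elsewhere the Protocol does treat the device as a possible cause in its own right: the summaries of earlier TDS-IM and TDS-ID use (Section 2.2.2.3) attribute events to the product, the device or both. The accountability section (6.1.2) covers only the DNA and the gp140 protein.

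For one class of event the scale then works the wrong way round. If the investigator cannot separate EP from DNA, the event counts. If the investigator is confident that EP caused it, the event can be graded 'Unlikely' and need not count. Protection of that participant then rests on discretion. This matters most for the intradermal device, which Section 2.2.2.3 reports as used in 20 volunteers to date.

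**Working it through.** The plan states no operating characteristic for either rule, so there is no figure to reproduce. The check is a reading of the text plus a count of exposures.

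**Step 1: trace an event through the rules.** Take a confirmed grade 3 or 4 event that lasts over 72 hours.

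- *Solicited, onset within 7 days.* Automatically an adverse reaction (8.1), so the relatedness condition is met whatever the cause. Both rules count it.
- *Any other event, DNA and EP equally plausible.* 'Possibly' related. Both rules count it.
- *Non-solicited, or solicited with onset after 7 days, and judged much more likely due to EP than to the DNA.* If study product is read as the DNA and the protein, this fits 'Unlikely', provided that it does not worsen with continued use, which that grade also requires. It then adds nothing to the 7.5 count and does not meet the 6.1.5 condition.

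The other hold in 7.5, for a SUSAR, does not close the third case, because 8.1 also ties a SUSAR to study product.

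**Step 2: count the EP applications** (Table 1, with 8 per group completing three DNA doses).

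- Group 1 (ID with EP): 8 × 3 × 1 = 24
- Group 2 (IM with EP): 8 × 3 × 1 = 24
- Group 3 (both with EP): 8 × 3 × 2 = 48
- Total: 24 + 24 + 48 = 96
- At doses 1 and 2, with another EP dose still to come in the same person: 96 × 2/3 = 64
- At dose 3, with no EP left to withhold: 96 − 64 = 32

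The individual rule can therefore prevent EP re-exposure after 64 of the 96 applications. After the other 32 it could only withhold the EP-free protein dose.

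**Step 3: compare the two thresholds.** Section 6.1.5 acts on one event in one person. Section 7.5 needs three participants: 3/24 = 12.5% of the planned number, or 3/30 = 10% at the exposure cap in Section 9. Any practical effect therefore falls mainly on 6.1.5.

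**Step 4: look for a rate.** The joint condition is grade 3 or 4, over 72 hours, not automatically related, and attributed to EP. The documents give no rate for it, so no probability is offered here. Section 2.2.2.3 describes paraesthesia as mild and lasting seconds to minutes, grade 3 local tenderness as transient, and severe fatigue in two subjects as gone by the next day. It reports no serious event attributed to the TDS-IM device or procedure.

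**Step 5: check the analysis.** The primary and secondary safety endpoints (Protocol 10.2; SAP 3.1.1 and 3.2.1) have no relatedness filter. An event put down to EP enters the group comparisons like any other.

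**The case against.** The strongest reply is that the gap depends on how the words are read. 'Vaccine', 'vaccine product' and 'study product' are never defined to exclude EP, and the Protocol often treats EP as part of vaccinating: Table 1 lists it under the method of immunisation, and the endpoints speak of vaccination with or without it. Automatic relatedness is tied to the act of immunisation and takes in effects plainly caused by delivery, such as discomfort and blisters. A reasonable investigator might count EP reactions. This stands as a possible reading. It is not the natural one, given the medicinal-product definition in 8.1 and the separate mention of the device in the background, and a mandatory rule should not depend on it.

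It is also fair that DNA and EP act at the same site within seconds, so excluding the DNA with confidence will be hard. The persistent injuries one would most expect from EP (pain, blistering, ulceration) are listed as solicited reactions in Appendix 2 and are automatically related if they start within 7 days.

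Safeguards without a strict product test remain: investigator discontinuation (6.1.5), PI and Trial Management Group (TMG) review of serious events with discontinuation to be considered (7.4.7), the sponsor's right to stop (7.5) and TMG monitoring of notable events (12.5). Section 7.1.1 adds referral to an independent specialist when relationship to the vaccine is uncertain. The separate MHRA device application mentioned in 2.2.2.3 may carry its own rules, but it is not among the documents. All of this narrows the gap. None of the safeguards seen here makes stopping mandatory.

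A reader might infer that EP harm in general escapes the stopping rules, or that the safety comparison between groups is compromised. The documents support neither: the first two cases in Step 1 count, and Step 5 shows that the endpoints are untouched.

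**Conclusion.** The point holds in a narrow form. On a literal reading, a confirmed, persistent grade 3 or 4 event that is not automatically related, and is judged much more likely due to EP than to the DNA, need not trigger either mandatory rule. The conclusion assumes that the three product terms mean the DNA and the protein, and that no device rule outside these documents fills the gap.

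The practical effect is mainly on the individual rule. The documents do not support a claim that such events are likely, that a hold would probably be missed, or that an investigator would in fact repeat EP after one. This is a wording gap in two safety rules for healthy volunteers. It is worth closing because closing it costs little, and confidence in the point is moderate.

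**What to change.** In Sections 6.1.5 and 7.5, make the condition read: *related to vaccine product and/or delivery device or administration procedure*. In 6.1.5, also state whether the week-20 protein dose may still be given after a device-only event. If it may not, that participant leaves the per-protocol set on which the primary immunogenicity analysis rests (Protocol 10.4.2.1; SAP 2.3), and may need replacing within the cap of 30.

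The cost is a protocol amendment, with REC and/or MHRA approval if it is substantial (Section 18), and possibly a few more safety reviews.

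Three additions are optional: a separate device-relationship field on the adverse event forms, if not already there; a matching row in SAP Tables 2 and 8 and a column in Table 7, whose relationship entries cannot now separate device-related from unrelated events; and a hold with expert review in 7.5 for serious unexpected events related to the device or procedure. The SUSAR definition itself is best left alone, since Section 8.1 states: "The definitions of the EU Directive 2001/20/EC Article 2 based on the principles of ICH GCP apply to this protocol".
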